7.2.1 ChangeToOne Policy versus the Bayesian Approach

Under the ChangeToOne policy, if a site-arm has "all zeros" data (that is, if all results for that site are zero in either the BEP or IFEP), one randomly chosen value of the zeros is changed into a one. By moving the data back from the edge of the outcome space the analysis method will be spared from having to deal with phenomena such as estimated variances of zero. Note that, under the alternative that the control arm has a lower success probability than the treated arm, this change will tend to move the arms closer together, and thus can be considered conservative.

Note that the protocol stated the ChangeToOne policy (see Section 12.8 of the protocol) would be used for the primary implementation outcome in the presence of any zero counts (i.e., no patient participants received ED-initiated BUP at a particular site in a particular evaluation period). A Bayesian approach (see Section 12.9 of the protocol), which has its own attractions and drawbacks, was also considered as a supportive analysis. Since the risk difference is of primary interest, the Bayesian approach will be used for estimating the risk differences, however the ChangeToOne policy will be used for the primary analysis to calculate a p-value based on the logistic regression model in Section 7.2. This logistic model assumes a linear effect of time on the log-odds scale, which corresponds to a time-varying risk difference scale. Thus the risk differences will be estimated at two time points, and may be calculated for other as well: (1) the last day for which one site was in the BEP and one site was in the IFEP (01/01/2019), and (2) the last day at which both enrolling sites were actively enrolling prior to the pause in enrollment due to the COVID-19 pandemic (03/02/2020).

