5.0 STUDY DESIGN

5.1 Figure 1: Overview: Study Activities

We will use a Hybrid Type 3 Effectiveness-Implementation design⁹ and a modified stepped wedge design^{1-4,10} to evaluate the effect of the IF on ED-initiated BUP with referral for ongoing MAT and its effectiveness. A Hybrid Type 3 design is recommended when there is strong face validity and strong initial evidence for the clinical and implementation interventions that would support generalizability; there is strong “implementation momentum” for adoption of the clinical intervention and evidence that the intervention being tested is feasible and supportable. In light of our prior work and the emphasis nationally on addressing the opioid epidemic, a Hybrid Type 3 design is warranted. The advantages of this design include a balanced provision of resources and support across all study sites, enrollment of comparable cohorts of participants during baseline evaluation and IF evaluation phases across all sites, and the completion of the proposed study in a short period of time (48 months). This overall short study time will minimize the potential impact of population related time trends and other time related factors such as changes in healthcare practice and policy. The randomized order of the timing of the IF at each site, offset by 3 month increments, is used to accommodate logistical constraints of a simultaneous implementation at all sites. The stepped wedge design is increasingly used to promote the implementation of evidence-based practice and is appropriate for evaluating interventions when there is evidence that the intervention is likely to be beneficial and when practical considerations require a sequential deployment of an intervention.^{4,10} At each of the four study sites, there will be a 12-month baseline evaluation period after the standard dissemination activity via a “grand rounds” education session, followed by a 6-month IF phase, followed by a 12-month IF evaluation period. A 6-month IF phase is required to allow adequate time to conduct the multiple components of the IF (see Table 1). An evaluation period of 12 months is necessary to enroll enough patients for adequate sample size. The number of patients should be similar during the baseline evaluation and the IF evaluation periods. The strategies included in the IF are iterative and continue throughout the IF and IF evaluation periods. The proportion of eligible study participants in each time period who are engaged in formal addiction treatment on the 30th day post enrollment will be assessed within each site and for the entire study cohort.

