3.3.6 Calendar Time

Calendar time for analysis is defined as the number of days since the site opened for enrollment in the baseline evaluation period. Below are the start and end dates for each site in each evaluation period. The start date is defined as the date the site was given access to the eClinical system to begin enrolling participants in the study for that particular evaluation period. The end date is defined as the last day the site was able to enroll participants in the EDC system for each evaluation period. Note that during the IFEP, enrollment was paused due to the COVID-19 public health measures put into place at two sites, Harborview Medical Center and University of Cincinnati. The days enrollment was paused will be considered as part of the primary analysis and several sensitivity analyses will be performed to account for this pause.

Site	Baseline Evaluation Period		IF Evaluation Period			
	Start Date	End Date	Start Date	Date Paused for COVID-19	Date Reopened for COVID-19	End Date
MA Johns Hopkins ED	4/10/2017	4/9/2018	10/9/2018	N/A	N/A	10/8/2019
NY Mount Sinai ED/Beth Israel	7/6/2017	7/5/2018	1/4/2019	N/A	N/A	1/5/2020
OV University of Cincinnati ED	10/9/2017	10/8/2018	4/8/2019	03/13/2020	6/10/2020	7/6/2020
PNW Harborview Medical Center ED	1/2/2018	1/1/2019	7/2/2019	03/3/2020	6/6/2020	10/4/2020

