16.1.3 Primary Implementation Outcome

**Table 13: Summary of Primary Implementation Outcome
by Evaluation Period**

Number	Baseline Evaluation Period (N=)	IF Evaluation Period (N=)	Total (N=)
Received ED-initiated BUP	N	N	N
Received referral for MAT	N	N	N
Received ED-initiated BUP with referral for ongoing MAT	N (XX.x%)	N (XX.x%)	N (XX.x%)

Table 14: Summary of Primary Implementation Outcome by Site and Evaluation Period

Number	Baseline Evaluation Period				IF Evaluation Period			
	MA Johns Hopkins ED (N=)	GNY Mount Sinai ED/Beth Israel (N=)	OV University of Cincinnati ED (N=)	PNW Harborview Med Center ED (N=)	MA Johns Hopkins ED (N=)	GNY Mount Sinai ED/Beth Israel (N=)	OV University of Cincinnati ED (N=)	PNW Harborview Med Center ED (N=)
Received ED-initiated BUP	N				N			
Received Referral for MAT	N				N			
Received ED-initiated BUP with Referral for Ongoing MAT	N (XX.x%)				N (XX.x%)			

Table 15: Analysis Results for Primary Implementation Outcome

GLMM		Bayesian Analysis		
Intervention Coefficient	p-value	Risk Difference Estimation Time Point	Risk Difference	95% Credible Interval
X.xx	x.xxx	Mid-point (day 632)	X.xx	X.xx; X.xx
		COVID-19 Pause (day 1423)	X.xx	X.xx; X.xx

**Table 16: Summary of Primary Implementation Outcome
by Sex and Evaluation Period**

Number	Baseline Evaluation Period		IF Evaluation Period	
	Male (N=)	Female (N=)	Male (N=)	Female (N=)
Received ED-initiated BUP	N		N	
Received Referral for MAT	N		N	
Received ED-initiated BUP with Referral for Ongoing MAT	N (XX.x%)		N (XX.x%)	

Table 17: Summary of Primary Implementation Outcome by Race and Evaluation Period

Number	Baseline Evaluation Period			IF Evaluation Period		
	White (N=)	Black/African American (N=)	Other (N=)	White (N=)	Black/African American(N=)	Other (N=)
Received ED-initiated BUP	N			N		
Received Referral for MAT	N			N		
Received ED-initiated BUP with Referral for Ongoing MAT	N (XX.x%)			N (XX.x%)		

**Table 18: Summary of Primary Implementation Outcome
by Ethnicity and Evaluation Period**

Number	Baseline Evaluation Period		IF Evaluation Period	
	Hispanic or Latino (N=)	Not Hispanic or Latino (N=)	Hispanic or Latino (N=)	Not Hispanic or Latino (N=)
Received ED-initiated BUP	N		N	
Received Referral for MAT	N		N	
Received ED-initiated BUP with Referral for Ongoing MAT	N (XX.x%)		N (XX.x%)	

**Table 19: Final Covariate Adjusted Model Analysis Results
for Primary Implementation Outcome**

Covariate ¹	N	Coefficient	95% Credible Interval
Study Phase			
BEP	N	[ref]	[ref]

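### One of the two risk differences planned for each primary outcome in SAP 2.0 is dated 2 March 2020, 426 days after the last baseline-period day, and the SAP does not say that its control rate is extrapolated

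*SAP*

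**What the plan says.** SAP 7.2 and 7.4 make the risk difference the main quantity to be estimated for each primary outcome. They take it from a logistic model with a site effect, a period effect and one linear time slope. SAP 7.2.1 notes the consequence: "This logistic model assumes a linear effect of time on the log-odds scale, which corresponds to a time-varying risk difference scale". It then fixes two evaluation dates and allows others:

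- First date: "the last day for which one site was in the BEP and one site was in the IFEP (01/01/2019").
- Second date: "the last day at which both enrolling sites were actively enrolling prior to the pause in enrollment due to the COVID-19 pandemic (03/02/2020").

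The shells for Tables 15, 21, 24 and 29 carry one row per date for each analysis. Table 15 labels the second row "COVID-19 Pause (day 1423").

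The calendar in SAP 3.3.6 gives the fourth site's baseline start and end as "PNW Harborview Medical Center ED 1/2/2018 1/1/2019". That end date is the latest baseline day at any site. Protocol 5.1 says of the intervention: "The strategies included in the IF are iterative and continue throughout the IF and IF evaluation periods".

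The Revised SAP text at the end of the SAP reports that the two periods hardly overlapped. It removes time from the model and makes a logistic regression on site and period the final model for both primary outcomes.

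**The concern.** A risk difference needs a rate in each period. On 2 March 2020 only the IF rate has data near it. The baseline rate on that day is whatever the fitted line says, and that line has a single slope for both periods.

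The same slope also has to describe any change within the IF evaluation period, because the model gives the IF effect one constant value. If IF takes hold gradually, part of the build-up is read as secular trend, and that raises the projected control rate. If the real secular trend bends after January 2019, the projection cannot follow it.

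At stake is one of the two risk differences prespecified for each primary outcome, presented with nothing to tell the reader that half of the contrast is unobserved.

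**Working it through.** **1. Dates.** The first site opened on 10 April 2017 ("MA Johns Hopkins ED 4/10/2017"). Counting that as day 1, 1 January 2019 is day 632, which matches the label in the shells. On the same clock 2 March 2020 is day 1058. The gap is 1058 − 632 = 426 days. The shells' day 1423 does not reproduce: 1423 − 1058 = 365, a year too late. That is a separate error, and correcting it would not remove the extrapolation. The clock itself also needs reconciling, because SAP 3.3.6 says "Calendar time for analysis is defined as the number of days since the site opened for enrollment in the baseline evaluation period". I use the trial-wide clock because it reproduces day 632.

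**2. Support.** The only stretch with both periods under observation runs from 9 October 2018 (first IF evaluation start) to 1 January 2019. That is 85 days, with one site in the IF evaluation period.

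**3. Formula.** At an average site, control(t) = logistic(α + βt) and RD(t) = logistic(α + βt + γ) − logistic(α + βt). On day 1058 no baseline patient lies nearby, so control depends wholly on linearity of βt and constancy of γ.

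**4. Size of the possible error.** I fitted site, period and linear time to expected rates on the SAP calendar, with 120 patients per site and period. The rates are assumptions for illustration. The last two rows hold the odds ratio at that of 5% against 25%.

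| Assumed truth | 1 Jan 2019: model / true (points) | 2 Mar 2020: model / true (points) |
|---|---|---|
| Control 5% throughout; IF rises on the logit scale from 5% on 9 October 2018 to 25% a year later, same calendar at all sites | 4.7 / 2.4 | 7.9 / 20.0 |
| Control rises from 5% to 10% by 1 January 2019, then stays level | 32.3 / 31.3 | 33.9 / 31.3 |
| Control 5% to 1 January 2019, then rises to 15% by 2 March 2020 | 20.6 / 20.0 | 30.7 / 37.8 |

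Absolute errors are 2.3, 1.0 and 0.6 points at the first date, against 12.1, 2.6 and 7.1 at the second.

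In the first row the fitted control rate on 2 March 2020 is 15.8% against a true 5%, and the fitted IF rate is 15.8 + 7.9 = 23.7% against 25%. Of the 12.1 points, 10.8 come from the projected control.

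Milder versions of the first row give smaller errors. A build-up from zero that is linear in probability gives 11.7 against 20. An IF rate starting at 15% and building to 25% gives about 17 against 20.

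**5. Interval width.** The SAP model was simulated with its stated priors on the SAP calendar: the four alternative scenarios of Protocol Table 4, ICC 0.01, 0.05 and 0.15, and 150 data sets each. A Gaussian site effect replaced the documents' data generator. Mean 95% interval widths with no trend at ICC 0.05:

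| Rates | Day 632 | Day 1058 |
|---|---|---|
| 0.05 / 0.25 | 0.287 | 0.237 |
| 0.15 / 0.25 | 0.267 | 0.240 |
| 0.25 / 0.40 | 0.300 | 0.262 |
| 0.25 / 0.50 | 0.308 | 0.265 |

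Over all 12 no-trend settings the risk-difference interval was narrower on day 1058 in 69–97% of data sets (median width ratio 0.67–0.93). The control rate's own interval was 1.13–1.89 times wider. Errors in the slope and in the period effect partly cancel in the difference.

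The pattern depends on the trend. At +0.4 logit per year the later interval was narrower in 29–79% of data sets. At +0.8 (ICC 0.05, two of the scenarios, 100 data sets each) it was narrower in about 30%, with mean widths of 0.288 against 0.319 for 0.05/0.25.

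**The case against.** **The interval.** A reader might infer that the interval is always narrower at the later date and so never warns. The calculations do not support that. In the growth-from-zero case, where the bias is largest, an approximate delta-method interval is wider at the later date (0.263 against 0.191). At 7.9 ± 13 points it still covers 20. Where there is no trend the model is right, and a narrower interval does not mislead. What stands is that the width does not track the loss of data support.

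**The growth scenario.** A reader might infer that the plan predicts a growing IF effect. Protocol 5.1 says only that the activities continue. A six-month IF phase precedes each IF evaluation period, so an effect of exactly zero on its first day is extreme, and the 15% start is the gentler case.

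**The retained date.** 1 January 2019 uses the same model and is not immune: 4.7 against 2.4 is a twofold relative error. The overlap midpoint, about 20 November 2018, gives 4.4 against 1.1. If the build-up runs on each site's own clock, the fitted risk difference is negative at both dates. Moving the date limits the extrapolation but does not repair a constant γ with a shared slope.

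**Disclosure and status.** SAP 7.2.1 does state the linearity and lists the overlap date first. The p-value does not depend on the date. The Revised SAP's final model has no dated contrast at all. These points limit the consequence. They do not supply the missing statement, and the Revised SAP does not withdraw the dated contrasts by name.

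**Conclusion.** The point holds for the time-adjusted analysis in SAP 2.0 (7.2, 7.2.1, 7.4; Tables 15, 21, 24 and 29). The 2 March 2020 risk difference sets an IF rate against a control rate projected 426 days past the last baseline observation, and the SAP does not say so.

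The dates are certain. The size of any error depends on assumed trends: from about 3 points in the milder cases to 12 in the extreme one. Errors on 1 January 2019 were smaller in absolute terms in the growth-from-zero and control-trend cases examined.

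The documents do not support the wider inference that the trial's final primary results are affected, because the final model contains no time term. This is a cheap improvement to the reporting of the time-adjusted analysis.

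**What to change.** In SAP 7.2.1 and the shells for Tables 15, 21, 24 and 29, remove the 03/02/2020 risk difference. Keep 01/01/2019, or use another date between 9 October 2018 and 1 January 2019. If a value late in the study is wanted, report the IF-period rate alone for that date. Alternatively, keep the contrast but label it as an extrapolation, and state that no site contributed baseline data after 1 January 2019.

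The cost is a sentence in 7.2.1 and the matching rows in four shells. The downside is that no risk difference is then given near the end of the study. The Revised SAP's model needs no change.

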7.3 Definition of Primary Effectiveness Outcome Measure

The primary effectiveness outcome is patient participant engagement in formal addiction treatment for OUD on the 30th day post-index ED visit. Engagement in formal addiction treatment for OUD is defined as enrollment and receiving formal addiction treatment for OUD on Study Day 30, assessed by patient self-report and confirmed by direct contact with the treating facility and/or treating. Formal addiction treatment for OUD will be those treatments consistent with the American Society of Addiction Medicine's levels of care (1-4) and will include a range of clinical settings including office-based providers of BUP or naltrexone, OTPs, intensive outpatient, inpatient, or residential treatments. Patients do not need to be receiving MAT on the Study Day 30 to be considered engaged in formal addiction treatment for OUD. Participation in a self-help program, such as Narcotics Anonymous, alone will not be considered as engagement in formal addiction treatment for OUD.

The primary effectiveness outcome measure is binary variable reflecting engagement in addiction treatment on the 30th day post-index ED visit. The outcome will be based on patient participant self-report on the Engagement in Treatment: Participant (ETP) form and confirmed by facility and/or treating clinician on the Engagement in Treatment: Facility (ETF) form. If a patient participant reports being in treatment (i.e., ETMEDTRT="1") but there is no confirmation from a facility or clinician (i.e., no ETFs are completed, or all ETENGAGE="0") then the individual is considered not engaged in formal addiction treatment for OUD. Similarly, if there is an ETF indicating the individual was engaged in treatment (i.e., ETENGAGE="1") but this is not in line with self-report (i.e., ETMEDTRT="0", or the facility name does not match the self-reported facility) then the patient participant is considered not engaged in formal addiction treatment for OUD. If there is no ETP completed or if an ETF is completed but the facility did not complete confirmation the individual was engaged in treatment (i.e., ETENGAGE is missing on an existing ETF), then the primary effectiveness outcome is considered missing. If the patient participant self-reports not being in treatment then they are considered not engaged in formal addiction treatment for OUD, regardless of any ETF forms completed. Lastly, if the ETP is not completed but there is an ETF completed, the primary effectiveness outcome measure is considered missing.

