11.9 Referral for Continuation of MAT

1. Baseline evaluation period: participants will be referred based on existing clinical practice at each site. The study will not inform practice.
2. IF and IF evaluation period: During the IF, linkages will be established with all community stakeholders offering MAT including office-based providers of BUP and OTPs. Referral options will be offered according to insurance status, study patient preferences and availability.

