Once eligibility is determined, the RA, who is knowledgeable about the study will explain the significant elements of the study to the potential participant. Included in the consent will be language allowing the ED RA to contact community-based providers and programs to determine the patient's engagement in formal addiction treatment status on the 30th day post enrollment. If the patient is able to converse and alert to person, place and time, the RA obtains signed, dated consent. A copy of the signed consent will be left with the participant. All persons obtaining consent must have completed appropriate training. The participant will be informed that their participation is voluntary and they may withdraw from the study at any time, for any reason without penalty. Individuals who refuse to participate or who withdraw from the study will be treated without prejudice. Study sites will be responsible for maintaining signed consent forms as source documents for quality assurance review and regulatory compliance.

The informed consent form must be updated or revised whenever important new safety information is available, or whenever the protocol is amended in a way that may affect participants' participation in the study.

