7.4 Analysis of Primary Effectiveness Outcome Measure

A mixed effects model will be used to compare the rates of patient engagement in formal addiction treatment for OUD on the 30th day post study enrollment between the baseline and IF evaluation periods. The model for the primary effectiveness will be used to compare the rates of engagement in formal addiction treatment for OUD on the 30th day post-index ED visit between the IFEP and BEP is:

$$\text{logit}(p_{si}) = \alpha + \beta t_{si} + \gamma f_{si} + r_s$$

where

- p_{si} is the probability of success of patient participant i at site s ,
- t_{si} is the calendar time of enrollment of patient participant i at site s ,
- f_{si} is the indicator of whether patient participant i at site s is in the BEP ($f_{si}=0$) or IFEP ($f_{si}=1$), and
- r_s is the random effect of site s , where $r_s \sim N(0, \sigma^2)$.

Note that calendar time is measured in days and defined in Section 3.3.6. In this model, γ captures the effect of implementation facilitation. The model will test a one-tailed hypothesis at the 0.05 level. The null and alternative hypotheses are:

$$H_0: \gamma \leq 0$$

$$H_a: \gamma > 0.$$

Similar to the implementation primary outcome, the main focus is the estimated Risk Difference (RD) defined as the difference between IF and Baseline engagement in treatment success rates, ($p_{IFEP} - p_{EP}$) with its 95% credible interval (CI). The estimated RD and its 95% CI will be obtained from the Bayesian approach as described in Section 7.3 for the primary effectiveness outcome. The SAS code will be analogous except p1 is now the proportion of patient participants engaged in formal addiction treatment for OUD on Study Day 30 during the BEP and p2 is the now the proportion during the IFEP.

The primary effectiveness outcome will be summarized by site and evaluation period with frequencies and percentages. Results of the Bayesian approach, that is the model specified above, will be presented tabularly with estimates and 95% credible intervals for the risk difference.

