7.5.3 Missing Data

It is anticipated that there will be no missing data expected for the primary implementation outcome since this entails data abstraction from the EHR after the index ED visit. One scenario in which missing data may arise is if the participant withdraws consent prior to medical record abstraction. To minimize missing data for the primary effectiveness outcome, the initial assessment conducted at the follow-up visit will be the ETP, which can be done over the phone to maximize availability. Per Section 12.10 of the protocol, any missing primary outcome data will be considered as failures (i.e., no provision of ED-initiated BUP, not engaged in formal addiction treatment for OUD on Study Day 30).

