16.1.4 Primary Effectiveness Outcome

Table 22: Summary of Primary Effectiveness Outcome by Evaluation Period

Number	Baseline Evaluation Period (N=)	IF Evaluation Period (N=)
Self-report Treatment Engagement	N	N
Facility confirmed Treatment Engagement	N	N
Missing primary effectiveness outcome (i.e., to be imputed as non-engaged)	N	N
Engagement in formal addiction treatment for OUD at Day 30	N (XX.x%)	N (XX.x%)

Table 23: Summary of Primary Effectiveness Outcome by Site and Evaluation Period

Number	Baseline Evaluation Period				IF Evaluation Period			
	MA Johns Hopkins ED (N=)	GNY Mount Sinai ED/Beth Israel (N=)	OV University of Cincinnati ED (N=)	PNW Harborview Med Center ED (N=)	MA Johns Hopkins ED (N=)	GNY Mount Sinai ED/Beth Israel (N=)	OV University of Cincinnati ED (N=)	PNW Harborview Med Center ED (N=)
Self-report Treatment Engagement	N				N			
Facility confirmed Treatment Engagement	N				N			
Missing primary effectiveness outcome (i.e., to be imputed as non-engaged)	N				N			
Engagement in formal addiction treatment for OUD at Day 30	N (XX.x%)				N (XX.x%)			

Table 24: Analysis Results for Primary Effectiveness Outcome				
GLMM		Bayesian Analysis		
Intervention Effect Coefficient	p-value	Risk Difference Estimation Time Point	Risk Difference	95% Credible Interval
X.xx	x.XXX	Mid-point (time = 632)	X.xx	X.xx; X.xx
		COVID-19 Pause (time = 1423)	X.xx	X.xx; X.xx

Table 25: Summary of Primary Effectiveness Outcome by Sex and Evaluation Period

Number	Baseline Evaluation Period		IF Evaluation Period	
	Male (N=)	Female (N=)	Male (N=)	Female (N=)
Self-report Treatment Engagement	N		N	
Facility confirmed Treatment Engagement	N		N	
Missing primary effectiveness outcome (i.e., to be imputed as non-engaged)	N		N	
Engagement in formal addiction treatment for OUD at Day 30	N (XX.x%)		N (XX.x%)	

Table 26: Summary of Primary Effectiveness Outcome by Race and Evaluation Period

Number	Baseline Evaluation Period			IF Evaluation Period		
	White (N=)	Black/African American (N=)	Other (N=)	White (N=)	Black/African American (N=)	Other (N=)
Self-report Treatment Engagement	N			N		
Facility confirmed Treatment Engagement	N			N		
Missing primary effectiveness outcome (i.e., to be imputed as non-engaged)	N			N		
Engagement in formal addiction treatment for OUD at Day 30	N (XX.x%)			N (XX.x%)		

**Table 27: Summary of Primary Effectiveness Outcome
by Ethnicity and Evaluation Period**

Number	Baseline Evaluation Period		IF Evaluation Period	

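### Engagement needs facility confirmation, which could differ between periods in either direction, and no planned model tests that step

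*SAP*

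**What the plan says.** SAP 7.3 combines the patient form (ETP) and the facility form (ETF). If a patient reports treatment but "there is no confirmation from a facility or clinician (i.e., no ETFs are completed, or all ETENGAGE='0') then the individual is considered not engaged". An ETF that exists with its engagement item blank makes the outcome missing, and under SAP 7.5.3 "any missing primary outcome data will be considered as failures". A facility confirmation whose facility name does not match the self-report is also scored not engaged.

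Protocol 11.9 separates the periods. At baseline, "participants will be referred based on existing clinical practice at each site. The study will not inform practice". Later, "During the IF, linkages will be established with all community stakeholders offering MAT including office-based providers of BUP and OTPs". Protocol 11.10 adds that IF feedback to clinicians will include whether patients entered treatment. SAP 2.3.3 says research assistants were told the intent of IF as each site made the transition.

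For the effectiveness outcome, SAP 7.4 fits time, period and a random site effect: "The model will test a one-tailed hypothesis at the 0.05 level". The Revised SAP section at the end of the SAP drops time and uses fixed effects for site and period. Supportive analyses (SAP 7.5) cover sex, race and ethnicity, the COVID-19 pause, a 44-day limit on when self-report was obtained, and engagement by ED-initiated BUP status. Tables 22-23 list counts by period in rows such as "Self-report Treatment Engagement" and its facility-confirmed counterpart.

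**The concern.** Every failure to obtain confirmation lowers the engagement rate, whatever its cause. If facilities answer more readily in one period, the period effect mixes a change in treatment with a change in verification. There are two reasons to ask. The intervention acts on the providers who do the confirming, and the staff who seek confirmation are not blind to period.

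SAP 7.5.4 already recognises surveillance bias in this outcome. Its remedy restricts only the timing of self-report and otherwise keeps the 7.3 definition, so the confirmation half is untested. The complete-case result in Table 32 does not help: it compares patients by BUP status, and a self-report with no ETF is coded zero rather than missing. For the same reason, the missing-outcome row of Tables 22-23 does not show how many self-reports had no ETF.

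**Working it through.** **Inputs from the documents.** Four sites with 120 patients per site and period, so 4 × 120 = 480 per period (Protocol 12.3, 12.6); one-sided 0.05 (SAP 7.4); baseline engagement 25%, IF engagement 40-50% (Protocol 12.5).

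**Assumptions.** Confirmation rates, since none is given. True engagement is equal in both periods, everyone engaged says so, and every unconfirmed self-report is a truly engaged patient.

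**Reproducing the plan's figure.** I simulated the planned schedule: 10 patients per month, 12 months baseline, 6 months IF, 12 months IF evaluation, 3-month offsets. The model was logistic with month, period and a random site intercept, with a one-sided Wald test. Clustering came from a latent-normal model, because the documents do not give the details of the cited simulation method. There were 600 replicates per setting, or 400 where marked *.

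- 25% vs 50%: power 0.97, 0.91, 0.93, 0.94, 0.96 at ICC 0, 0.05, 0.1, 0.2, 0.3. The stated value above 0.8 (Protocol 12.9.1) reproduces.
- 25% vs 40%: 0.70*, 0.58, 0.65* at ICC 0, 0.1, 0.3, in line with the low power acknowledged in Protocol 12.8.
- 25% vs 25%, ICC 0.1: rejection 0.05 in the SAP 7.4 model and 0.04 in the site-plus-period model.

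**Differential confirmation.** Let q be true engagement and c the confirmation probability.

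Observed rate = q × c; spurious difference = q × (c_IF − c_base). Fixing the observed baseline at 25% gives q = 0.25 / c_base.

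- 80% vs 90%: q = 0.25/0.80 = 0.3125; IF rate = 0.3125 × 0.90 = 28.1%; difference 3.1 points.
- 70% vs 90%: q = 0.25/0.70 = 0.357; IF rate = 0.357 × 0.90 = 32.1%; difference 7.1 points.
- 60% vs 90%: q = 0.25/0.60 = 0.417; IF rate = 0.417 × 0.90 = 37.5%; difference 12.5 points.

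Probability of rejecting with no true effect (ICC 0.1):

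| Confirmation, baseline vs IF | SAP 7.4 model | Site + period model |
|---|---|---|
| 80% vs 90% | 0.11 | 0.28 |
| 70% vs 90% | 0.23 | 0.79 |
| 60% vs 90%* | 0.45 | 0.995 |

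**Check by hand.** For 80% vs 90%, SE = √[(0.25×0.75 + 0.281×0.719)/480] = 0.0285, so z = 0.03125/0.0285 = 1.10 and Φ(1.10 − 1.645) = 0.29, close to the site-plus-period result. On the planned schedule, period and month correlate 0.934 within site, a variance inflation of 1/(1 − 0.934²) ≈ 7.8. The SE grows by √7.8 = 2.79, z falls to 1.10/2.79 = 0.39, and Φ(0.39 − 1.645) = 0.11, as simulated. Removing time is what raises the exposure.

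**Upper limit.** To create the whole planned rise from 25% to 40%, confirmation would have to rise 0.40/0.25 = 1.6-fold, for example from 60% to 96%. For 25% to 50% it would have to double.

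**The case against.** The strongest reply is that verification is a research procedure set out alike for both periods. Patients who will not allow contact with their provider are excluded (Protocol 7.2). Consent covers "allowing the ED RA to contact community-based providers and programs to determine the patient's engagement in formal addiction treatment status" with no distinction by period (Protocol 14.4). All reported engagement is to be verified with the provider (Protocol 14.8.1), and the assessment schedule is the same in both periods (Protocol Table 2). The links in Protocol 11.9 are for referral. This stands: the documents do not show that confirmation differed.

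A reader might infer that the bias must favour IF. The documents do not support that. SAP 7.5.4 worries that earlier enrollees had more chance of reaching the outcome, which would favour baseline. The COVID-19 pauses fell only in the IF period, at two sites (SAP 3.3.6), and could have made facilities harder to reach. Nor was baseline free of contact: external facilitators then worked with site investigators to identify champions related to community programs (Protocol 11.10).

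A facility denial is also legitimate grounds for a zero; catching those is what verification is for. Only the unanswered share is in question. Finally, Tables 22-23 would expose a gross divergence, and the outcome is treated as secondary (SAP 9.0). Both points limit the weight of the matter. But those tables do not separate denial from non-response, and they feed no model or interpretation rule.

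**Conclusion.** The point holds as an untested possibility, not as a demonstrated bias. SAP 7.3 scores non-response by a facility as non-engagement, confirmation could plausibly differ by period, and every planned analysis of the period effect keeps that rule.

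Under the stated assumptions, a rise from 80% to 90% adds about 3 points and takes one-sided rejection from 0.05 to about 0.11 in the SAP 7.4 model, or 0.28 in the revised model. From 70% to 90% it adds about 7 points, with 0.23 and 0.79. A fall in confirmation would push the estimate the other way. The figures assume planned enrolment and no correct denials, so they are illustrations.

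A simple two-proportion test with 40% truly engaged in both periods gives rejection of 0.37 (80% vs 90%) and 0.85 (70% vs 90%). A reader might take these as the error rate of the plan. They are not: that test has no time term, and at those confirmation rates the SAP 7.4 model gives far less. Nor could a modest difference in confirmation produce the full planned effect.

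**What to change.** Leave the primary definition unchanged and add two items to SAP 7.5.4.

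1. Refit the effectiveness model, in the form used for the primary effectiveness result, to self-reported engagement alone (ETMEDTRT=1, missing counted as failure).
2. In Tables 22-23, by site and period, split the self-reported engaged patients into confirmed, denied (all ETENGAGE=0) and no completed facility response (no ETF, or ETENGAGE blank). Footnote any facility-name mismatches.

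If the no-response share differs by period, report the range of the effect between the confirmed and self-reported definitions. The split by site is also useful because the Revised SAP section reports a site-by-period interaction (p=0.021); it would show whether confirmation varied along with it.

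The cost is a paragraph of SAP text, one model and a few table rows, from forms already collected. As the Revised SAP section already discusses results, an addition made now should be labelled post hoc. The downside is that self-report has its own error, which could also differ by period, so the refit is a second view and not a replacement.
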